3.4 Framework

All comparisons will be presented in a superiority testing framework.

3.5 Statistical interim analyses and stopping guidance

An interim report was created when 50% of patients were randomized and had completed the last scheduled visit. An independent statistician, who was blinded to the treatment allocation, created the interim report. The statistician reported to an independent Data Safety Monitoring Board (DSMB). The DSMB was blinded to all data (stratified groups were denoted as group “A” and group “B”) and discussed the results of the interim analysis with the statistician. No between-group tests were conducted for the two primary outcomes or for any other endpoints. The DSMB also reviewed safety events. The DSMB recommended the trial continue to completion and decided not to unblind itself to the interim data.

3.6 Timing of the final analysis

The final analysis will occur within 6 months of completing data collection; the final analysis is planned for mid-2020.

3.7 Timing of outcome assessments

Telephone calls to participants are made at 1 week, 1 month, 2 months, 4 months and 5 months post-randomization. After a baseline set of measurements, urine samples, blood samples, and SF-36 form completion occurs at the 3-month and 6-month visits. The study drug is stopped immediately after the 6-month follow-up visit; a final telephone call is made to participants 7-months post-randomization.

4. Statistical Principles

4.1 Confidence intervals and P values

The overall type I error rate will be fixed at 0.05. The Hochberg procedure will be used to test each of the two-sided hypothesis tests for the two primary outcomes. The largest of the two P values will be compared to $\alpha = 0.05$, and if this test is non-significant, the smaller P value will be compared to $\alpha/2 = 0.025$. If the largest P value is < 0.05 , both hypothesis tests will be rejected.³⁰ If both of the two primary outcomes are tested at the 0.05 significance level, 95% CIs will be reported; if either of the primary outcomes are tested at the 0.025 significance level, 97.5% CIs will be reported for both tests.

All secondary analyses will be considered exploratory in nature and P values will not be reported; 95% CIs will be reported without adjustment for multiple testing.

4.2 Adherence and protocol deviations

Protocol compliance was assessed through pill counts and interviews at each follow-up visit. Protocol deviation is defined as missing taking the study medication over 7 or more days during any 4-week period. Patients who miss taking the medication over 7 or more days during any 4-week period will meet with an investigator to discuss ways of improving adherence. We will report the number and percentage of participants who experience at least one protocol deviation, overall and by treatment group. We will report the median (25th and 75th percentiles) number of doses missed over the entire study period, overall and by group.

Study treatment discontinuation is defined as missing study medication for ≥ 4 weeks consecutively. We will report the number and percentage of participants who discontinue the study, overall and by group.

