3.1 Trial design

MPAC-CKD-1 is a parallel group, double-blind, placebo-controlled randomized trial. Participants were randomly assigned to receive either microparticle curcumin or matching placebo in a 1:1 ratio. Microparticle curcumin was administered at 90 mg per day (three 30 mg capsules once daily) for 6 months. The dose remained constant over the study period.

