6.4 Harms

Study medication discontinuation

We will report the number and percentage of patients who discontinue the study medication by group, as study medication discontinuation can suggest that the drug is poorly tolerated.

In addition, we will report the number and percentage of participants who experience the following side effects which are assessed using standardized case report forms at the 3-month and 6-month follow-up visits.

Minor side-effects

In rare cases, curcumin has been reported to cause minor nausea, headache, diarrhea, yellow stool, temporary giddiness, localized swelling of the skin (contact dermatitis), or hives (urticaria). The number and percentage of patients who experience each of these side effects will be reported by treatment group, and the number of minor side effects experienced by each patient will be summarized by group. For each minor side-effect, a Chi-squared test will be used to test whether the percentage of patients experiencing the minor side-effect is equal between groups; P values will be tested at the 0.05 significance level.⁴¹

Bleeding

In the 1990s, two studies described curcumin's *in vitro* activity against platelet function.^{42,43} Further *in vitro* work has since identified curcumin's ability to inhibit platelet activation, which could increase the risk of bleeding.⁴⁴⁻⁴⁸ However, when applied in animal models, curcumin appears to have no effect on clinically relevant bleeding,⁴⁹⁻⁵³ and in a recent study of oral curcumin loading immediately prior to abdominal aortic aneurysm repair, no significant risk of bleeding was identified.⁵⁴ The number and percentage of patients experiencing a bleeding event during the course of the study will be reported by treatment group. A Chi-squared test will be used to test whether the percentage of patients experiencing at least one bleeding event is equal between groups; P values will be tested at the 0.05 significance level.⁴¹

Hypoglycemia

Curcumin is a potent inhibitor of CYP2C9, which could increase the pharmacologic effects of some anti-diabetic medications such as sulfonylureas.⁵⁵ Although curcumin has been studied extensively in the

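### The SAP's definition of treatment discontinuation leaves out permanent stops in about the last 4 weeks of dosing and includes long pauses that resume; the effect on the tolerability count is probably small

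*Combined protocol and SAP*

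**What the plan says.** SAP 4.2 gives the only definition: "Study treatment discontinuation is defined as missing study medication for ≥ 4 weeks consecutively". It has no separate category for a permanent stop, and it does not require that the drug stays stopped. The next sentence reports something else: "We will report the number and percentage of participants who discontinue the study, overall and by group".

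SAP 3.1 sets dosing at 6 months, and SAP 3.7 fixes its end: "The study drug is stopped immediately after the 6-month follow-up visit".

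SAP 6.4 reports the number and percentage discontinuing study medication by group, "as study medication discontinuation can suggest that the drug is poorly tolerated". It gives no other definition. The published protocol lists study agent discontinuation and safety among its secondary outcomes and explains that tolerability needs to be understood before a larger trial.

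Several other outputs bear on the point:
- SAP 4.2 reports a second adherence measure by group: "Protocol deviation is defined as missing taking the study medication over 7 or more days during any 4-week period". It also summarizes missed doses over the whole study by group.
- SAP 5.3 includes discontinuation of the intervention in the flow diagram.
- SAP 5.4 reports withdrawal from the study separately, with reasons. It recognizes that a participant can stop the drug without withdrawing consent.
- SAP 6.4 tabulates and tests minor side effects, bleeding and hypoglycemia separately.

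**The concern.** A count that serves as a tolerability signal should include a patient who gives up the drug for good, whenever that happens. Under the stated rule it cannot do so near the end of treatment. Doses after the 6-month visit are not due and so cannot be missed, and a run of 4 missed weeks no longer fits. A permanent stop because of a side effect in that period is left out. A patient who is off drug for 5 weeks and then returns is included, although that says less about tolerability.

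At stake is a listed secondary outcome meant to inform the next trial. The flow-diagram count in 5.3 is also affected, since it has no other definition to draw on. The wording slip in 4.2 adds a second problem: the section defines stopping the drug and then reports leaving the study, which 5.4 treats as a different group.

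**Working it through.** The plan states no discontinuation rate, so there is no figure to reproduce. The check is of the definition's reach.

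**Inputs from the documents.** Discontinuation threshold: 4 weeks = 28 days (SAP 4.2). Dosing period: 6 months (SAP 3.1), taken as 26 weeks = 182 days. Deviation threshold: 7 days in any 4-week period (SAP 4.2). Arm size: 518 / 2 = 259 (SAP 3.3, 1:1 allocation).

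**Assumed, because the documents are silent.** Permanent-stop rate of 5% to 20% per arm. Stop times either evenly spread, or declining exponentially from the start with a half-life of 13, 8 or 4 weeks.

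**Step 1: the blind window.** 28 / 182 = 15.4% of the dosing period.

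**Step 2: share of permanent stops that falls in it.** With even timing the share is 15.4%. With early-loaded timing and half-life h weeks, λ = ln 2 / h and

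share = (e^(−22λ) − e^(−26λ)) / (1 − e^(−26λ)).

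For h = 13: λ = 0.0533, and the share is (0.3094 − 0.2500) / (1 − 0.2500) = 7.9%.

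**Step 3: patients left out per arm** = 259 × stop rate × share.

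| Stop timing | Share in last 4 weeks | 5% stop | 10% stop | 20% stop |
|---|---|---|---|---|
| Even | 15.4% | 2.0 | 4.0 | 8.0 |
| Half-life 13 weeks | 7.9% | 1.0 | 2.1 | 4.1 |
| Half-life 8 weeks | 4.9% | 0.6 | 1.3 | 2.5 |
| Half-life 4 weeks | 1.1% | 0.1 | 0.3 | 0.6 |

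In percentage points of the arm, this is 0.8 to 3.1 with even timing, and about 0.06 to 1.6 with early-loaded timing.

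**Step 4: who is still visible elsewhere.** A patient who stops with 7 to 27 days left has missed at least 7 days within a 4-week period and is a protocol deviation. With even timing that is 21 / 28 = 75% of those left out. Stops in the last week, 7 / 182 = 3.8% of all permanent stops, need not appear in either count, but their missed doses still enter the missed-dose summary.

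**Step 5: effect on the comparison of arms.** Suppose true permanent-stop rates of 15% and 10% (assumed), the same even timing in both arms, and no pauses. The counted rates are 15% × (1 − 0.154) = 12.7% and 10% × (1 − 0.154) = 8.5%. The ratio stays at 1.5, and the difference shrinks from 5.0 to 4.2 points.

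**Step 6: pauses.** The number of interruptions of 4 weeks or more that resume cannot be computed, because no pause rate is given. This error raises the count, whereas the late-stop error lowers it.

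**The case against.** The best defense is that the plan does not depend on this one count. Protocol deviations catch most late stoppers, the missed-dose summary includes all their missed doses, and a late stop for diarrhea or bleeding should appear in the side-effect tables, which are tested by group. Discontinuation itself is only described; it is not among the safety outcomes that Supplemental Table 1 lists for testing. No efficacy estimate uses the definition: the primary analysis is by intention to treat, and the per-protocol set rests on pills taken in the first three months. All of this stands, and it limits the size of the problem.

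It does not repair the count. The deviation figure mixes late stoppers with patients who missed some doses and carried on, and a median of missed doses does not show who stopped for good.

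Three stronger readings are tempting, and the documents do not support them:
- A reader might infer that late stoppers are never counted anywhere, or are counted as having completed treatment. The first is true of the discontinuation count only. For the second, the SAP defines no completed-treatment category.
- A reader might infer that the tolerability comparison is distorted. One rule applies to both blinded arms, and the comparison is biased only if the timing of stops or the frequency of long pauses differs between arms. The documents give no data on either.
- A reader might infer that the rule hides everyone off drug at the 6-month samples. Anyone off for 4 weeks or more at that point meets the definition, and anyone off for 1 to 4 weeks is a deviation. What remains true is that no planned output identifies these patients as a group.

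**Conclusion.** The concern holds as a definitional fault. Followed literally, SAP 4.2 with 3.7 makes the count in 6.4 omit permanent stops in about the last 15% of dosing and include pauses of 4 weeks or more that resume, and no other section corrects this. The omission is probably small: about 2 to 8 patients per arm with even timing, and 0 to 4 with early-loaded timing. Both ranges rest on an assumed 5% to 20% stop rate, 259 per arm and a 26-week dosing period. The share would exceed 15% if stops clustered late. The over-count from pauses is unknown, so the net direction of the error is too. Bias between the arms is not shown, and the primary analyses, sample size and type I error are untouched. The mismatch in 4.2 between stopping the drug and leaving the study is a wording slip that should be corrected at the same time.

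**What to change.** Change the SAP wording as follows. This alters reporting only, not how patients are managed.

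1. Define study medication discontinuation as cessation with no resumption before the 6-month visit, whatever the time left. Use that definition in 4.2, 5.3 and 6.4.
2. Report interruptions of 4 weeks or more followed by resumption on a separate line, by arm.
3. In 4.2, make the reporting sentence refer to discontinuing the study medication. Keep withdrawal of consent separate, as in 5.4.
4. Where the data allow, give by arm the reason for stopping and the number off drug at the 6-month samples.

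Item 4 is conditional. SAP 4.2 mentions pill counts and interviews at follow-up visits, and the protocol's nonadherence section says that reasons will be catalogued. Neither document says that a last-dose date, or drug status on the sampling day, is recorded. Items 1 and 2 will likewise have to be derived from those pill counts and interviews.

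The cost is a little extra derivation work, and the reported discontinuation rate may change slightly in either direction.

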4.3 Analysis populations

We will conduct all primary analyses according to the intention-to-treat (ITT) principle. We will conduct an exploratory per-protocol analysis for each of the two primary outcomes consisting of patients who were adherent to their randomly assigned treatment, as defined by taking $\geq 80\%$ of pills given during the first three months of follow-up (or were adherent until they died or developed ESRD if this occurred within the first three months).

5. Trial Population

5.1 Screening data

Patient characteristics were not recorded for patients who were assessed for eligibility but were either (i) not eligible or (ii) not interested in participating.

5.2 Eligibility

Patients with an eGFR between 15 and 60 mL/min per 1.73 m² and overt albuminuria, defined by either a 24-hour urine collection with a minimum of 300 mg of protein or a urinary albumin-to-creatinine ratio equivalent to a daily excretion of albumin of at least 300 mg, were recruited. Patients with conditions that may potentially be exacerbated by the use of micro-particle curcumin (active peptic ulcer disease, hepatobiliary disease, history of significant bleeding) or who take medications that may interact with micro-particle curcumin were excluded (**Table 1**).

5.3 Recruitment

The participant recruitment and randomization flow diagram will follow CONSORT recommendations.³¹ We will report the number of participants approached to participate in MPAC-CKD-1, as well as the number of participants who: (i) declined to participate, (ii) were approached but were found to be ineligible, (iii) were randomized, (iv) received the allocated intervention, (v) were lost to follow-up or discontinued the intervention, (vi) were included in the final analysis.

5.4 Withdrawal/follow-up

Participants who stop taking the study drug, but do not withdraw consent to participate in the study, will continue with the study's scheduled telephone visits and may replace remaining in-person visits with telephone visits. Participants wishing to withdraw consent will be asked to complete the closing telephone visit (scheduled for 4 weeks after study drug completion) 4 weeks after withdrawal of consent. The number and percentage of participants who withdraw from the study will be reported overall and by group. Reasons for study withdrawal will be presented in a supplementary document.

5.5 Baseline patient characteristics

Table 2 contains a summary of baseline (pre-randomization) characteristics to be summarized by group. Continuous baseline characteristics will be summarized as mean (standard deviation [SD]) and categorical baseline characteristics will be summarized as number (percent).

6. Analysis

See **Supplemental Table 1** for information on changes made to the analysis section of the MPAC-CKD-1 study protocol published in The Canadian Journal of Kidney Health and Disease.³² These changes were made without knowledge of the trial results.

6.1 Outcome definitions and analysis methods

Two primary outcomes

We will assess two outcomes: the between-group difference in 6-month urinary albumin-to-creatinine ratio (log-transformed, measured in mg/mmol), and the 6-month change in eGFR (6-months post-randomization minus pre-randomization, measured in mL/min per 1.73m²). Placebo will serve as the referent group in all analyses.

Albuminuria: Albuminuria will be measured using urinary albumin-to-creatinine ratio from first morning urine samples. At each visit (pre-randomization, and 3- and 6-months post-randomization), urinary albumin-to-creatinine ratio is measured on two consecutive days and the average of the two values will be computed. The average of the two values will be log-transformed using the natural logarithm. A summary of the pre-treatment, 3-month and 6-month urinary albumin-to-creatinine ratio measurements will be provided. The geometric mean ratio of 6-month urinary albumin-to-creatinine ratio will be estimated using linear regression, where the outcome is the log-transformed average of two 6-month follow-up visit urinary albumin-to-creatinine ratio measurements minus log-transformed average of two pre-treatment urinary albumin-to-creatinine ratio measurements, adjusting for a treatment indicator variable and the log-transformed average of two baseline urinary albumin-to-creatinine ratio measurements. The 95% or 97.5% CI for the geometric mean ratio will be presented.³³

eGFR: eGFR will be calculated using the CKD-EPI formula, which includes patient age, sex, race (black vs. other), and the serum creatinine concentration.³⁴ We will summarize the pre-randomization, 3-month and 6-month eGFR measurements by group. We will estimate the between-group difference in change in eGFR (6-month eGFR minus pre-randomization eGFR), expressed in mL/min per 1.73m², using linear regression. The outcome is the change in eGFR (6-month value minus pre-randomization value) and the treatment indicator variable will be included as a covariate. The 95% or 97.5% CI for the between-group difference in change in eGFR will be presented.

Secondary outcomes

Health-related quality of life: We will summarize health-related quality of life scores determined by the RAND version of the 36-Item Short Form Health Survey (SF-36) administered pre-randomization and at 3-months and 6-months post-randomization. The physical composite summary (PCS) score and mental composite summary (MCS) score of the SF-36 will be examined separately. The between-group difference in change in each composite score, 6-month value minus pre-randomization value, will be reported with 95% CIs. Beyond preservation of kidney function are several other potential mechanisms by which curcumin may benefit quality of life, including potential benefits on depression and chronic pain.^{35,36}

Glycemic control: We will summarize the percentage of glycated hemoglobin pre-randomization and at 3-months and 6-months post-randomization. We will present the between-group difference in change in percentage of glycated hemoglobin (6-month value minus pre-randomization value) among patients with diabetes mellitus (diabetes mellitus was a stratification variable in the randomization), with the 95% CI.

Progressive CKD, ESRD and death: We will report on the outcome of progressive CKD, ESRD, and death, first as a composite outcome, and then as separate components. We will define ESRD as an eGFR <15 mL/min/1.73 m² or the initiation of renal replacement therapy, which includes chronic dialysis or transplantation; progressive CKD will be defined as an eGFR loss of $\geq 30\%$ (anytime during follow-up from the pre-randomization baseline value) or ESRD. We expect less than 10% of participants will experience these outcomes by 6 months. Our focus is to document any trends to inform the expected event rate for future studies. Each outcome (progressive CKD, ESRD and death) will be summarized separately as number (percentage) of patients with the event by group. The HR of progressive CKD (as its own outcome) will be estimated using Cox proportional hazards regression, treating death as a competing event. The same approach will be used for the outcome of ESRD. Each estimate will be reported with 95% CIs.

Serum curcumin levels: To confirm our micro-particle curcumin was bioavailable,¹⁶ and to strengthen any relationship between micro-particle curcumin and any outcomes we identify, serum levels of curcumin and its major metabolites were measured in the first 30 participants 3 months after randomization (including patients taking micro-particle curcumin and those taking placebo). Serum curcumin and its major metabolites will be summarized in the first 30 participants randomized, by group. The between-group difference in average serum curcumin levels measured 3-months post-randomization will be reported with the 95% CI.

Pre-specified subgroup analysis

We will conduct an exploratory subgroup analysis based on a higher or lower estimated risk of kidney failure, using the kidney failure risk equation.¹⁹ Participants with a 2-year risk of ESRD less than 10% will be classified as lower risk, and patients with a risk of 10% or more will be classified as higher risk. For both primary outcomes, separate regression models with an interaction term between randomization group and the kidney failure risk category indicator variable will be used. The 6-month albumin-to-creatinine ratio geometric mean ratio will be reported for each kidney failure risk equation group, and the difference in change in eGFR will be reported for each kidney failure risk group, along with 95% CIs.

Missing data for reasons other than death will be handled using model-based multiple imputation methods (as the primary method to handle missing data in all analyses). Additional analyses will be performed to confirm that conclusions are not sensitive to assumptions about the missing-data mechanism.³⁷ In the primary analyses, outcomes that are missing due to death will not be imputed (expected in less than 5% of patients). In sensitivity analyses, to account for missing values due to death we will (i) use multiple imputation to impute missing outcomes; (ii) use single imputation where a missing 6-month albumin-to-creatinine ratio will be imputed as a doubling of the baseline albumin-to-creatinine ratio value, and 6-month eGFR will be imputed as half of the pre-randomization eGFR. Pre-randomization data, the treatment variable, stratification variables, and data collected at both the 3-month and 6-month visits will be included in the multiple imputation models. For patients missing both urinary albumin-to-creatinine ratio measurements at a particular visit, one urinary albumin-to-creatinine ratio will be imputed as the average value; urinary albumin-to-creatinine ratio will be imputed on the log scale. If a patient is missing one of the two urinary albumin-to-creatinine ratio measurements at a particular visit, the single observed value will be taken as the average urinary albumin-to-creatinine ratio for that visit and no imputation will occur. Estimates from each complete dataset will be combined using standard methods.³⁸ The imputation model will allow for an interaction effect between the treatment variable and the kidney failure risk equation indicator variable.³⁹

For all primary and secondary outcomes, the pre-randomization, 3-month and 6-month measurements will be summarized by group as mean (standard deviation) and median (25th and 75th percentiles) or number and percentage, depending on whether the variable is continuous or categorical.

Randomization reliably removes random differences between treatment groups when at least 1000 participants are included.⁴⁰ With the size of our sample, it is possible that imbalances may arise between the treatment groups on important characteristics that may influence outcomes. In sensitivity analyses, we will repeat the two primary analyses while (i) accounting for randomization strata (centre and pre-randomization diabetes); (ii) accounting for randomization strata and adjusting for variables associated with disease progression including age, sex, tobacco use, blood pressure, baseline use of angiotensin-converting enzyme inhibitors or angiotensin receptor blockers, and baseline use of aldosterone antagonists. We do not anticipate that accounting for randomization strata and/or adjustment for pre-randomization variables will change the results in any meaningful way.

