2.2 Objectives

Our primary objective is to assess the between-group difference in two outcomes examined separately: urinary albumin-to-creatinine ratio (6-month post-randomization value) and change in eGFR from pre-randomization to 6-months post-randomization.

Our secondary objective is to assess: i) the between-group difference in health related quality of life (as assessed by a 6-month change in the RAND version of the 36-Item Short Form Health Survey [SF-36]), ii) the between-group difference in glycemic control (as assessed by a 6-month change in glycated hemoglobin among patients with diabetes mellitus; diabetes mellitus was a stratification variable in the randomization), iii) the risk of a composite outcome of progressive CKD, ESRD or death with micro-particle curcumin versus placebo, and iv) the between-group difference in measured serum levels of curcumin and its major metabolites (to be done on measurements taken 3-months after randomization in the first 30 participants; being done to assess curcumin bioavailability).^{14,16}

We will also conduct a pre-specified exploratory subgroup analysis of the primary outcomes based on a higher or lower estimated risk of future kidney failure (based on the kidney failure risk equation¹⁹).

3. Study Methods

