In our preliminary work on urinary albumin-to-creatinine ratio testing, we found patients eligible for MPAC-CKD-1 had a mean initial urinary albumin-to-creatinine ratio of 128.3 mg/mmol.²⁶ Over 3 months, we observed a mean increase in the urinary albumin-to-creatinine ratio of 30.7 mg/mmol and found the standard deviation of the change to be 69.2 mg/mmol. Enrolling a total of 518 patients and

accounting for 5% loss to follow-up allows for 82% power ($\alpha = 0.025$) to detect a geometric mean ratio of 0.75, assuming a standard deviation of the 6-month log-transformed albumin-to-creatinine ratio of 1.0.²⁷ For the between-group difference in change in eGFR (6-month eGFR minus pre-randomization eGFR), we will have 81% power ($\alpha = 0.025$) to exclude a difference of 1.65 mL/min per 1.73 m² between treatment and control groups (using a standard deviation of the change of 5.8 mL/min per 1.73 m²). In general, the average decline in eGFR in albuminuric CKD patients is 2 to 4 mL/min per 1.73 m² per year (with a standard deviation of 3-4 mL/min per 1.73 m² per year).^{28,29} The standard deviations used in these sample size calculations are based on overall standard deviations observed in the MPAC-CKD-1 study.

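### The eGFR co-primary model omits pre-randomization eGFR; adding that one term would probably cut variance by about 1-8%, and could gain nothing

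*Combined protocol and SAP*

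**What the plan says.** SAP Section 2.2 sets the eGFR objective as the between-group difference in "change in eGFR from pre-randomization to 6-months post-randomization". Section 6.1 specifies the model: "The outcome is the change in eGFR (6-month value minus pre-randomization value) and the treatment indicator variable will be included as a covariate". No other term is named. Supplemental Table 1 supports the literal reading, because it expects the regression to give practically the same estimates and P values as the t test it replaces. That is so only if no covariate is added.

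The other co-primary is treated differently in the same section. Its outcome is the change in log albumin-to-creatinine ratio, modelled by "adjusting for a treatment indicator variable and the log-transformed average of two baseline urinary albumin-to-creatinine ratio measurements".

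The sensitivity analyses in Section 6.1 add the randomization strata, and then strata together with "adjusting for variables associated with disease progression including age, sex, tobacco use, blood pressure", baseline use of ACE inhibitors or ARBs, and baseline use of aldosterone antagonists. The list is worded as open, but it does not name baseline eGFR. For the subgroup analysis, "separate regression models with an interaction term between randomization group and the kidney failure risk category indicator variable will be used"; baseline eGFR is not named there either.

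**The concern.** A change score subtracts the whole baseline value, which amounts to fixing the slope of 6-month eGFR on baseline eGFR at 1. If the true slope is below 1, because of measurement noise or regression to the mean, the change score over-corrects. Change is then correlated with baseline, and that correlation stays in the residual as avoidable variance. Putting baseline in the model lets the data set the slope.

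The same mechanism bears on chance imbalance. If the arms differ at baseline by some amount, the unadjusted estimate shifts by -(1 - slope) times that amount. This is the variance component just described seen from another side, and should not be counted as a second harm.

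At stake is some precision on a co-primary whose planned power is only 81%. The validity of the test is not in question. With baseline as a covariate, the treatment coefficient is still the between-group difference in change, so the Section 2.2 objective is untouched.

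**Working it through.** **Inputs from the documents.** SAP Section 3.3: 518 enrolled, 5% loss, difference 1.65, SD of change 5.8, alpha 0.025. Section 4.1: two-sided tests. Section 3.1: 1:1 allocation. Section 5.2: "Patients with an eGFR between 15 and 60 mL/min per 1.73" m².

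**Not in the documents.** Baseline SD, 6-month SD and the correlation between visits. These are assumed below.

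**Step 1: the plan's own figure.** Analysed per arm: 518 × 0.95 / 2 = 246. Standard error = 5.8 × √(2/246) = 0.523. Noncentrality = 1.65 / 0.523 = 3.155. The noncentral t with 490 degrees of freedom gives power 81.7% (normal approximation 82.0%), against 81% stated. The difference detectable with 80% power is 1.62.

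**Step 2: effect of adjustment.** Residual variance = 5.8² × (1 - r²), where r is the correlation of change with baseline. The price is one degree of freedom, about 1/490 = 0.2% of variance. By r alone:

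| r (absolute) | variance fall | power |
|---|---|---|
| 0 | 0% | 81.7% |
| 0.1 | 1% | 82.2% |
| 0.2 | 4% | 83.4% |
| 0.3 | 9% | 85.5% |

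**Step 3: equal SDs s at both visits (assumption).** Slope = 1 - 5.8²/(2s²); variance fall = 5.8²/(4s²).

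| s | slope | variance fall | power |
|---|---|---|---|
| 10 | 0.832 | 8.4% | 85.2% |
| 12 | 0.883 | 5.8% | 84.2% |
| 13 | 0.900 | 5.0% | 83.8% |

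A uniform spread over 15-60 would have SD 45/√12 = 13.0, which is why 13 is included.

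**Step 4: baseline restricted, follow-up not (assumption).** Take an underlying normal distribution with mean 30-40 and SD s of 10-20. Truncate baseline to 15-60, leaving variance V. Solve (1 - b)²V + s²(1 - b²) = 5.8² for the slope b. The variance ratio is then s²(1 - b²)/5.8².

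| mean, s | baseline SD | 6-month SD | b | variance fall | power |
|---|---|---|---|---|---|
| 35, 10 | 9.18 | 9.44 | 0.830 | 7.3% | 84.8% |
| 35, 14 | 10.84 | 11.43 | 0.913 | 2.7% | 82.9% |
| 30, 20 | 11.77 | 12.66 | 0.957 | 0.7% | 82.1% |

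Over the whole grid the 6-month SD is 2.9-7.6% larger than baseline, variance falls by 0.7-7.3%, and the 80%-power difference is 1.56-1.61.

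**Step 5: where the gain vanishes.** r = 0 when the 6-month variance equals the baseline variance plus 5.8². For baseline SD 10, 12 or 13, the 6-month SD must be larger by 16%, 11% or 10%. In the other direction, a 6-month SD 5% below baseline gives falls of 11-14% for the same baseline SDs, but the eligibility restriction makes that less likely.

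**Step 6: imbalance, to confirm it is the same component.** With s = 12, the standard error of the baseline difference is 12 × √(2/246) = 1.08. A one-standard-error imbalance shifts the unadjusted estimate by (1 - 0.883) × 1.08 = 0.126. As a share of variance, 0.126²/0.523² = 5.8%, which is the fall found in Step 3.

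**Step 7: simulation (10,000 runs per setting).** Power, change score against adjusted: 81.5% v 84.9% (equal SDs of 10), 81.6% v 83.8% (12), 81.2% v 82.2% (truncated, mean 35, s = 14). Rejection under the null, against a nominal 0.025: 0.023 v 0.022 (equal SDs of 12) and 0.024 v 0.025 (truncated, s = 14).

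**The case against.** The planned comparison is unbiased under randomization and meets its stated power, so what remains is a preference for baseline adjustment worth a few power points at most. That stands, and it is why the point is offered as an improvement and not as a fault.

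The size cannot be derived from the documents, and the upper end may be optimistic. Section 3.3 cites an SD of 3-4 per year for eGFR decline. If all of that were true slope variation independent of baseline, it would add variance of 1.5² to 2.0² = 2.25 to 4.0 at 6 months. The 8.4% figure would then drop to 7.3-6.5%, and the 2.7% figure to 2.3-2.1%. This also stands. It lowers the range slightly without changing its order, and nil remains possible.

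The two co-primaries may differ for a reason. Supplemental Table 1 says the albuminuria model follows a newly published method for that measure, while the eGFR regression was meant to leave the published t test essentially unchanged. That explains why the albuminuria model changed. It does not discuss baseline eGFR or say why it should be left out.

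Changing a primary model late has a cost beyond one term: the stated equivalence with the t test no longer holds, several dependent models change, and a second eGFR estimate exists that could fall on the other side of a threshold. This is partly right. However, the sponsor has already revised both primary models at this stage and states that "These changes were made without knowledge of the trial results". The same route is open for this change, and naming one primary and one supportive estimate in advance removes the ambiguity. A milder alternative, adding baseline eGFR only to the second sensitivity model, would leave the primary analysis no more precise.

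**Conclusion.** The point holds as a free improvement. The eGFR co-primary is modelled without its baseline value, the parallel co-primary is not, and the documents do not explain the omission. Under reasonable assumptions about SDs the documents do not report, adjustment would reduce variance by roughly 1-8% and raise power from 81.7% to about 82-85%, a gain of about 0.3 to 3.5 points. The gain depends on the correlation of change with baseline and is nil if that correlation is zero, in which case the loss is about 0.2% of variance. The planned analysis is valid, its stated power is correct, and no conclusion of the trial is put at risk by leaving it as it is.

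**What to change.** Before unblinding, change the primary eGFR model in SAP Section 6.1 to: change in eGFR = treatment + pre-randomization eGFR. Carry the same term into the eGFR sensitivity, subgroup and per-protocol models. Keep the unadjusted difference as a supportive estimate and list it explicitly, because Section 6.3 plans no additional analyses. Record the change and its reason in Supplemental Table 1, and amend the remark there about equivalence with the t test.

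The sponsor can size the gain without by-group results. Section 3.3 says: "The standard deviations used in these sample size calculations are based on overall standard deviations observed in the MPAC-CKD-1 study". The pooled correlation of change with baseline can be computed from the same overall data. It should be reported as the expected gain and not used to decide whether to adjust, so that the choice does not appear driven by the data.

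Cost: one model term, one degree of freedom, one further row in Supplemental Table 1 and one supportive estimate. The change score already requires the pre-randomization value, so nothing new is collected.
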